3.2. Primary Endpoint(s)/Outcome(s)

- Differences in innate immune signatures between D0, D1, and D7 and each dose of Zoster vaccine recombinant, adjuvanted in both age cohorts.

3.3. Secondary Endpoint(s)/Outcome(s)

- Differences in related adverse events and serious adverse events between each dose of Zoster vaccine recombinant, adjuvanted, in both age cohorts.

3.4. Exploratory Endpoint(s)/Outcome(s)

- The changes in transcriptomics, metabolomics and immune cell populations between D0 (before vaccination) and D1, D3, D7, D14 and D30 after each dose of Zoster vaccine recombinant, adjuvanted, in both age groups.
- The changes in the phenotype of T cell responses and the kinetics of these changes between D0 (before vaccination) and D7, D14 and D30 after each dose of Zoster vaccine recombinant, adjuvanted, as well as D180 and D270+ (optional visit), in both age groups.
- The changes in the magnitude of activated B cells, antibody secreting cells and memory B cells and the kinetics of these changes between D0 (before vaccination) and D7, D14 and D30 after each dose of Zoster vaccine recombinant, adjuvanted, as well as D180 and D270+ (optional visit), in both age groups.
- The changes in VZV serology between D0 (before vaccination) and D14 and D30 after each dose of Zoster vaccine recombinant, adjuvanted, as well as D180 and D270+ (optional visit), in both age groups.
- The changes in specificity, magnitude and phenotype of VZV-specific (gE and other antigens) T cells and the kinetics of these changes between D0 (before vaccination) and 7, 14, 30 days after each dose of Zoster vaccine recombinant, adjuvanted, and at D180 and D270+ (optional visit), in both age groups.
- The changes in magnitude of VZV-specific B cells and the kinetics of these changes between D0 (before vaccination) and 7, 14, 30 days after each dose of Zoster vaccine recombinant, adjuvanted, and at D180 and D270+ (optional visit), in both age groups.
- Microbiome parameters in stool collected at baseline. These will be correlated to the immune responses to the Zoster vaccine to assess whether the stool microbiome may be related, and possibly influence immune responses.

3.5. Stratification, Randomization, and Blinding/Masking

60 subjects (n=30: 50-60 years old, n=30: ≥ 70 years old) will be enrolled in the study and will receive two doses of Zoster Vaccine Recombinant, Adjuvanted (Shingrix®) at D0 and D60. There will be no randomization, study participant or clinical study personnel blinding, or masking.

3.5.1. Procedure for Unblinding/Unmasking

Not applicable for clinic staff. Laboratory staff will be blinded as to the age group that each participant belongs to

4. Selection of Participants and Clinical Sites/Laboratories

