Blood samples will be collected at D0 (pre-vaccination) and D1, D3, D7, D14, D30, D60 (second dose of vaccination), D61, D63, D67, D74, D90, D180 and D270+ (optional visit) post vaccination to study innate and adaptive immunity responses. Samples from the different cohorts will be labeled to preserve the blind of the laboratory staff running the assays during the first phase of the analysis. Stool samples will be collected at baseline to assess the microbiome.

[figure not shown]

Figure 1: Study design

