4.4. Selection of Clinical Sites/Labs

The study will be conducted at The Hope Clinic, the clinical arm of the Emory Vaccine Center at Emory University.

Address:

[name]
[name]

Samples may be processed at the following laboratories:

[name], Stanford University, California
[name], La Jolla Institute, California
[name], Emory University, Atlanta, GA

5. Known and Potential Risks and Benefits to Participants

5.1. Risks of Investigational Product or Intervention as cited in Investigator Brochure or Package Insert

In clinical trials involving a pooled cohort of 29,305 subjects above 50 years of age who received at least one dose of Shingrix[®] (n=14,645) or saline (n=14,660) administered to a 0- and 2-month schedule, the following adverse reactions have been seen:

- Local adverse events: pain (78%), redness (38.1%), swelling (25.9%)

- General adverse event: myalgia (44.7%), fatigue (44.5%), headache (37.7%), shivering (26.8%), fever (20.5%), and gastrointestinal symptoms (17.3%).

The incidence of solicited local and general symptoms was lower in subjects aged 70 years and older compared with those aged 50 to 69 years.

The majority of solicited local adverse reactions and general adverse events seen with Shingrix® had a median duration of 2 to 3 days.

Headache and shivering were reported more frequently by subjects after Dose 2 (28.2% and 21.4% respectively) compared with Dose 1 (24.4% and 13.8% respectively). Grade 3 solicited general adverse events (headache, shivering, myalgia and fatigue) were reported more frequently by subjects after Dose 2 (2.3%, 3.1%, 3.6% and 3.5% respectively) compared with Dose 1 (1.4%, 1.4%, 2.3% and 2.4% respectively).

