8.6. Visit Windows

Study visits should take place within the time limits specified below:

D0 (first dose of vaccination) D1, D3, D7 (+/-1), D14 (+/-2), D30 (+/-7), D60 (+7) (second dose of vaccine), D61, D63, D67 (+/-1 from second vaccination), D74 (+/-2 from second vaccination), D90 (+/-7 from second vaccination), D180 (+/-14 from first vaccination, for each scheduled visit. An optional visit at any time point past 9 months (D270 +) from first vaccination may also take place.

This is also indicated on the Table of Events.

9. Mechanistic Assays

1. Expression of cytokines and chemokines via FACS. This assay will detect the expression profile of cytokines and chemokines to determine the innate response to vaccination.
2. Analysis of innate immune responses using FACS to assess numbers of activated innate cell populations. This assay will detect innate cell population activation including DC subsets, monocyte subsets, and NK cells, since these cell subsets are known to play crucial roles in immune regulation.
3. Molecular signatures of vaccination using RNA-seq on 2 mL of whole blood. This assay will determine the changes in mRNA and miRNA expression in whole blood. Results will be interpreted with use the method Significance Analysis of Microarrays (SAM) to determine change over baseline.
4. Microbiome Analysis: Analysis of microbiome diversity in the stool samples will be performed by Illumina MiSeq V4 16S Sequencing. Sample preparation will involve quantification and normalization of genomic DNA, PCR amplification of V4 hypervariable region of the bacterial 16S rDNA gene, PCR product quantification and library construction. Illumina MiSeq V4 16S sequencing and Bioinformatics analysis will involve V4 hypervariable region paired-end amplicon sequencing (MiSeq: 2x250 cycles). Filtering and trimming of all sequencing data will be done and mapped to taxonomic databases to identify bacterial composition in samples.
5. Levels of VZV-specific IgG/IgA/IgM antibody titers in the plasma by ELISA. This antibody assay will be used to quantify the levels of VZV-specific IgG and IgA in the plasma. Positive results will be assessed by 2X the negative control wells.
6. Number of VZV-specific IgG/IgA/IgM plasmablasts via ELISPOT. This cellular assay will be used to quantify the number of VZV-specific and total IgG/IgA/IgM antibody secreting cells in the blood. Positive results will be assessed by > 5 spots per million PBMCs.

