13.3 Measures to Minimize Bias

This is an open-label mechanistic study. No randomization will be conducted.

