13.4 Analysis Plan

Data from the study will be analyzed using the statistical software R. High-throughput data will be analyzed using appropriate methods, either by stand-alone software or modules in leading statistical software, e.g. the Bioconductor in the R framework. For cytokine data, missing values will be dealt with using multiple imputations. For gene expression and metabolomics data, nearest neighbor method and local least squares may be used to fill missing values. Unsupervised learning techniques such as PCA, PLSDA, clustering, and factor analysis will be used for the visualization and identification of global patterns. For descriptive endpoints, we will generate summary statistics, and visualize the data using histograms and boxplots when applicable. For the identification of innate signatures, the two age groups will be analyzed separately.

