13.4.2 Primary Analysis of Primary Endpoint

We will use paired t-test or Wilcoxon signed-rank test to compare each immune parameter (innate immune responses) between D1 and D7 after first dose of vaccine, between D61 and D67 after second dose of vaccine, and D0 and D60 (at each dose of Zoster vaccine). The choice of the test will depend on the normality of the data, as judged by normal Q-Q plots.

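### The stated laboratory blind covers age group, which is constant within every pair, and leaves visit day without stated masking, so it protects none of the within-person contrasts in the primary analysis

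*Combined protocol and SAP*

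**What the plan says.** Section 3.5.1 gives the scope of the blind: "Laboratory staff will be blinded as to the age group that each participant belongs to". Section 3.1 says that samples from the cohorts are "labeled to preserve the blind of the laboratory staff running the assays during the first phase of the analysis", which ties the coding to cohort and limits its duration. Section 13.3, on minimizing bias, adds only this: "This is an open-label mechanistic study. No randomization will be conducted".

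The primary analysis in section 13.4.2 uses paired t-tests or Wilcoxon signed-rank tests, parameter by parameter, "between D1 and D7 after first dose of vaccine, between D61 and D67 after second dose of vaccine, and D0 and D60". The primary endpoint in sections 3.2 and 13.2 names D0, D1 and D7, so comparisons of D0 with D1 and D7 are also implied, although 13.4.2 does not list them. Section 13.4 adds: "For the identification of innate signatures, the two age groups will be analyzed separately".

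Section 9 lists among the innate assays "Analysis of innate immune responses using FACS to assess numbers of activated innate cell populations", covering dendritic cell, monocyte and NK subsets. Section 4.4 says "Samples may be processed at the following laboratories" and names three institutions, without allocating assays, participants or visits among them. Section 10 provides for frozen plasma and cryopreserved PBMC. Sections 9 and 10 contain no rule on coding of visit day, gating or batch layout. Section 13.4.3 lists no supportive analysis of the primary endpoint.

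**The concern.** A blind protects a comparison only if it hides the factor being compared. Here the factor in every primary test is visit day. Age group is the same on both sides of each pair, so concealing it helps comparisons between cohorts and does nothing for D1 against D7, D61 against D67, D0 against D60, or the implied D0 against D1 and D7.

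Gating of activated cell subsets in flow cytometry involves judgement. A reader who knows that a file comes from the day after vaccination may place gates differently from one who believes it is a baseline or a day-7 file. If that tendency runs the same way across participants, the paired test reads it as a change over time. Everyone is vaccinated, so no unvaccinated group would show the same drift and expose it. FDR adjustment would not remove it either, because the bias is already in the p-values.

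**Working it through.** **1. Which contrasts does the age blind protect?**

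| Comparison | Factor that differs within the pair | Hidden by the stated blind? |
|---|---|---|
| D1 vs D7 (13.4.2) | visit day | not stated |
| D61 vs D67 (13.4.2) | visit day | not stated |
| D0 vs D60 (13.4.2) | visit day (both pre-dose) | not stated |
| D0 vs D1, D0 vs D7 (implied by 3.2 and 13.2) | visit day (pre- vs post-dose) | not stated |
| 50-60 vs ≥ 70 years | age group | yes, for the first phase |

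The contrasts written in 13.4.2 are post-dose against post-dose or pre-dose against pre-dose. The pre/post contrast comes from the endpoint wording.

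**2. Reproduce the plan's figure.** Inputs from section 13.7: n = 30 per age group, two-sided alpha 0.01, effect size 0.66, power 80%. For a paired t-test, power = P(|T| > c), where T is noncentral t with 29 df and noncentrality d√n.

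- c = t(0.995; 29) = 2.756
- noncentrality = 0.66 × √30 = 3.615
- power = 79.7%, which agrees with the stated 80%

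**3. The same formula for a marker with no true change.** Let s be a systematic reader shift, in SDs of the paired difference, with the same sign and size in every participant. The documents give no value for s, so the range is an assumption. Noncentrality is s√30. The last column multiplies by 50, the upper bound on the number of immune parameters in section 13.7, and assumes that all are null and share the shift.

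| s (assumed) | s√30 | Rejection rate | Expected false positives in 50 |
|---|---|---|---|
| 0 | 0 | 1.0% | 0.5 |
| 0.10 | 0.548 | 2.1% | 1.0 |
| 0.20 | 1.095 | 6.2% | 3.1 |
| 0.25 | 1.369 | 10.0% | 5.0 |
| 0.30 | 1.643 | 15.3% | 7.6 |

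Section 13.7 accepts alpha 0.01 because fewer than one false positive is expected. Under these assumptions a shift of 0.1 SD already brings the count to about one.

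**4. Run effects that do not follow visit day.** Accrual is staggered over 18 months (section 8.1), so run shifts will tend to differ in sign between participants. Simulation with n = 30, alpha 0.01, and a mean-zero run shift with SD 0.5 of the paired-difference SD gives null rejection rates of about 1.0% if each participant has an independent shift, 2.8% if three participants share each shift, and 5.3% if five do. The main cost is power. If run variance adds a fraction r to the variance of the paired difference, the effective effect size is 0.66/√(1 + r):

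- r = 0.25: 0.59, power 68.1%
- r = 0.50: 0.54, power 58.2%
- r = 1.00: 0.47, power 43.4%

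**The case against.** Several points on the other side stand.

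- **Silence is not disclosure.** No section says that laboratory staff will see the visit day. A reader might infer that the label is open to them, but the documents support only that masking is not stated. Section 15.2 refers to protocol-specific MOP requirements, and coding, gating templates or batch layout may be set out in the MOP, which is not among the documents reviewed.
- **Run and laboratory effects.** A reader might infer that any laboratory or run difference between days looks like a vaccine effect and inflates false positives as in step 3. That would need alignment with visit, for example all D0 samples in one run and all D1 samples in another, and nothing in the documents plans this. Scattered run shifts behave as in step 4.
- **Three laboratories.** A reader might infer that one participant's samples for one assay will be split between sites. The list in section 4.4 is equally consistent with one site per assay.
- **Scope.** The reader-judgement argument applies to flow gating and has little force for RNA-seq or LC/MS. It is also weaker for D0 against D60, where both samples are pre-dose and the expected direction is less obvious.
- **Threshold.** Section 13.7 introduces alpha 0.01 for sample size and, in the gene-expression context, says FDR will be used in the analysis. The 1% baseline may therefore not be the operating level.

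None of this answers the central point. The sponsor chose to mask the laboratory and wrote the rule down, but the factor it masks is not one that the primary tests compare. A rule in the MOP would answer the concern if sections 3.1 and 3.5.1 cited it.

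**Conclusion.** The gap holds as a matter of design. The stated blind protects between-cohort comparisons and no primary within-person contrast, visit day is not stated to be masked, and there is no control arm to reveal a visit-aligned reader shift. This is exposure to bias, not evidence that bias has occurred.

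The size is unknown. The increase from 1% to about 2%, 10% or 15% at 0.1, 0.25 or 0.3 SD rests on an assumed expectation-driven shift in the same direction in every participant, on 30 participants per test, and on the sample-size alpha. It concerns the flow-cytometry readouts. It should not be applied to run or laboratory effects in general, and the laboratory allocation and batching questions are secondary because they may be operational detail held elsewhere.

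**What to change.** **Main change (sections 3.1 and 3.5.1).** Extend the existing coding so that visit and dose, as well as age group, are hidden from those who gate, count and quality-check the data until those steps are locked. For assays run fresh, where the day of the draw may be evident at the bench, apply this to gating of the stored FACS files. Section 13.3 can then name this as the measure against reader bias.

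**Secondary change (sections 4.4 and 9).** For stored material, run the visits being compared for a participant, for example D0 to D7 and D60 to D67, in the same laboratory and batch where feasible. If the MOP already has such a rule, cite it.

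**Cost.** No extra samples or participants are needed. Clinic staff, or someone else outside the reading team, must hold the code, and stored-sample runs must wait until the compared visits are complete. Limiting the batch to the compared visits avoids holding samples until D180 or the optional later visit.

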4.1. Rationale for Study Population

Older adults (50-60 years old and ≥ 70 years old) who have no history of HZ and are naïve to previous HZ vaccination will be enrolled to receive two doses of Shingrix®. Subjects will receive vaccination during the ACIP-recommended window for HZ vaccination (at 0 and 2 months), but separated in time from all other vaccines (influenza, pneumococcal, etc.). There will be no intentional recruitment of any specific racial groups.

4.2. Inclusion Criteria

1. Subject must be able to understand and provide informed consent.
2. Adults aged 50-60 years, or community dwelling adults aged 70 years and above.

4.3. Exclusion Criteria

1. Inability or unwillingness of a subject to give written informed consent or comply with study protocol.
2. Receipt of immune products:
 - Receipt of blood products within 6 months prior of the first dose of the study Zoster vaccine or expected receipt through 6 months after vaccination with the second dose of the study Zoster vaccine^.
 - Receipt of any vaccine within 4 weeks prior to vaccination with any of the two doses of the study Zoster vaccine or expected receipt within 4 weeks after vaccination with any of the two doses of the study Zoster vaccine^.
 - Receipt of any Zoster or varicella vaccines at any time prior to study entry.
3. Subject taking any non-topical antiviral therapy with activity against herpes viruses, including but not limited to acyclovir, famciclovir, valacyclovir, and ganciclovir 3 days prior to each vaccination or 14 days after^.
4. Prior history of shingles.
5. Presence of certain co morbidities or immunosuppressive states such as:
 - Chronic medical problems including (but not limited to) insulin-dependent diabetes, severe (at the discretion of the investigator or study physician) heart, lung, liver, or kidney diseases; auto immune diseases; severe gastrointestinal diseases; and uncontrolled hypertension.
 - Impaired immune function or chronic infections including (but not limited to) HIV, hepatitis B or C, tuberculosis, organ transplant, cancer, current and or expected receipt of chemotherapy, radiation therapy, steroids [i.e., ≥ 20 mg of prednisone given daily or on alternative days for 2 weeks or more in the past 90 days^{^,^}]; (nasal (less than 1mg/day of fluticasone equivalent inhaled corticosteroid is allowable) and topical steroids are allowed)], antitumor necrosis factor agents, or any other immunosuppressive therapy, anatomic or functional asplenia, congenital immunodeficiency.
6. Conditions that could affect the safety of the subjects such as:
 - Severe reactions to prior vaccinations.
 - History of anaphylactic/anaphylactoid reaction to any component of the vaccines.

- History of bleeding disorders.

7. Any acute illness, including any fever (≥ 100.4 F [≥ 38.0 C], regardless of the route) within 3 days prior to study entry[^].
8. Social, occupational, or any other condition that in the opinion of the investigator might interfere with compliance with the study and vaccine evaluation.
9. Alcohol or drug abuse and psychiatric conditions that in the opinion of the investigator would preclude compliance with the trial or interpretation of safety or endpoint data.
10. Use of investigational drugs within 12 months of participation.
11. Past or current medical problems or findings from physical examination or laboratory testing that are not listed above, which, in the opinion of the investigator or study physician, may pose additional risks from participation in the study, may interfere with the subject's ability to comply with study requirements or that may impact the quality or interpretation of the data obtained from the study.
12. Women of childbearing potential.

Notes:

[^]An individual who initially is excluded from study participation based on one or more of the time-limited exclusion criteria (e.g., acute illness, receipt or expected receipt of live or inactivated vaccines) may be considered for enrollment once the condition has resolved as long as the subject continues to meet all other entry criteria.

^{^^}Subjects receiving ≥ 20 mg/day of prednisone or its equivalent daily or on alternate days for more than 2 weeks may enter the study after therapy has been discontinued for more than 3 months.

4.4. Selection of Clinical Sites/Labs

The study will be conducted at The Hope Clinic, the clinical arm of the Emory Vaccine Center at Emory University.

Address:

[name]
[name]

Samples may be processed at the following laboratories:

[name], Stanford University, California
[name], La Jolla Institute, California
[name], Emory University, Atlanta, GA

5. Known and Potential Risks and Benefits to Participants

5.1. Risks of Investigational Product or Intervention as cited in Investigator Brochure or Package Insert

In clinical trials involving a pooled cohort of 29,305 subjects above 50 years of age who received at least one dose of Shingrix[®] (n=14,645) or saline (n=14,660) administered to a 0- and 2-month schedule, the following adverse reactions have been seen:

- Local adverse events: pain (78%), redness (38.1%), swelling (25.9%)

- General adverse event: myalgia (44.7%), fatigue (44.5%), headache (37.7%), shivering (26.8%), fever (20.5%), and gastrointestinal symptoms (17.3%).

The incidence of solicited local and general symptoms was lower in subjects aged 70 years and older compared with those aged 50 to 69 years.

The majority of solicited local adverse reactions and general adverse events seen with Shingrix® had a median duration of 2 to 3 days.

Headache and shivering were reported more frequently by subjects after Dose 2 (28.2% and 21.4% respectively) compared with Dose 1 (24.4% and 13.8% respectively). Grade 3 solicited general adverse events (headache, shivering, myalgia and fatigue) were reported more frequently by subjects after Dose 2 (2.3%, 3.1%, 3.6% and 3.5% respectively) compared with Dose 1 (1.4%, 1.4%, 2.3% and 2.4% respectively).

5.2. Risks of Investigational Product or Intervention cited in Medical Literature

No other data exists in the medical literature on risks of vaccination with Shingrix®, since it is a newly approved vaccine by the FDA (October 20th, 2017).

5.3. Risks of Other Protocol Specified Medications

We do not anticipate the use of any other medication; however, should anaphylactic or hypersensitivity reactions occur, epinephrine (1:1000) and diphenhydramine injections are readily available at the Hope Clinic during vaccine use.

Epinephrine injection can be associated with high blood pressure, arrhythmia, lightheadedness, nervousness, restlessness, tremor, shortness of breath and diaphoresis. The frequency of these side effects is not defined. Diphenhydramine injection may be required to treat possible allergic reactions and its use can be associated with low blood pressure, arrhythmia, confusion, dizziness, sedation, restlessness, diarrhea, nausea and urinary retention. The frequency of these side effects is also not defined.

When facing a medical emergency, the clinic staff will follow the institutional SOP by calling 911 first. If needed, the subject will be transferred to Emory University Emergency Department for further care.

Subjects are allowed to receive acetaminophen or nonsteroidal anti-inflammatory drugs (NSAIDs) if they experience a moderate to severe local or systemic side effects after vaccine administration. The use of these medications will be recorded as concomitant medications.

